1.2.3. Exploratory Objective (Group 2 only)

To explore the pharmacodynamic effects of cemiplimab in tumor biopsies obtained at baseline, during treatment, and at progression in BCC patients treated with cemiplimab and to assess predictive potential and correlation to clinical response for biomarkers of interest including but not limited to:

- Tumor RNA expression
- Number and distribution of TILs (CD8+ T cells, CD4+ T cells, T regulatory cells, and tissue permitting, other subtypes such as B cells, myeloid-derived cells, NK cells, etc.)

- Expression levels (mRNA and/or protein) of PD-L1, GITR, and LAG-3, and possibly other check-point modulators
- Mutations in known oncogenes and potential tumor neoantigens
- Tumor mutation burden

1.2.4. Modifications from the Statistical Section in the Final Protocol

Added TTR, DCR, and dDCR as secondary endpoints.

1.2.5. Modifications from the Approved Statistical Analysis Plan

This is the second version of the SAP, based on the study protocol of R2810-ONC-1620 Amendment 4 dated July 29, 2019.

The main changes from SAP 1.0 dated Nov 8, 2016 (based on original protocol) include:

1. For the analysis of overall response rate in Group 1 (metastatic BCC), the statistical plan was revised so that the lower bound of the 95% confidence interval would exclude a clinically insignificant ORR of 15% in order to declare that the study treatment is effective.
2. The dose of cemiplimab has been changed from 250 mg Q3W to 350 mg Q3W.
3. Clarified the details of the timing of the data cut for the primary analysis for Group 2. Added an interim analysis for Group 1.
4. Post treatment follow-up was extended for an additional 1 year, for a total of approximately 1.5 years after completion of the treatment at the end of extended follow-up (unless the patient enters retreatment).

The following table outlines the main changes made to the SAP:

SAP 1.0 (Nov 8, 2016)	SAP 2.0 (current version)	Protocol Amendment version and Rational
The benchmarks for clinically meaningful response rates of Group 1 (metastatic BCC) was 10%.	The benchmarks for clinically meaningful response rates of Group 1 (metastatic BCC) was changed to 15%.	Change added in Protocol Amendment 2 (Mar 23, 2017). The benchmark is more stringent based on FDA feedback.
Planned dose of cemiplimab was 250 mg Q3W.	Planned dose of cemiplimab was changed to 350 mg Q3W.	Change added in Protocol Amendment 2 (Mar 23, 2017) based on modeling of exposure. No patient was enrolled prior to Protocol Amendment 2.
Post-treatment follow-up was 6 months.	Post-treatment follow-up was extended for an additional 1 year, for a total of approximately 1.5 years.	Change added in Protocol Amendment 4 based on FDA feedback in order to increase stringency in capturing duration of response.
No interim analysis	Added an interim analysis for Group 1. Clarified the details of timing of the data cutoff for the primary analysis for Group 2	Changes added in Protocol Amendment 4 in order to perform interim analysis of Group 1 at the time of primary analysis of Group 2.

2. INVESTIGATION PLAN

2.1. Study Design

There are two study groups for this clinical trial, which will be analyzed independently. For each group, this is a phase II, non-randomized, multi-center pivotal trial evaluating the efficacy and safety of cemiplimab.

- Group 1: Patients with metastatic BCC. These patients are required to have histologic confirmation of distant BCC metastases (e.g. lung, liver, bone, or lymph node). Group 1 includes patients with both nodal metastatic and distant metastatic disease.
- Group 2: Patients with unresectable locally advanced BCC. These patients are required to have disease that is considered inoperable or to have medical contraindication to surgery or radiation, or have not achieved disease control with these treatments.

2.2. Statistical Hypothesis

For the primary endpoint of ORR, the following null hypothesis and alternative will be tested at 2-sided significance level of 5% for Group 1 and Group 2, respectively.

Group 1: H_0 : ORR = 15% vs H_1 : ORR \neq 15%

Group 2: H_0 : ORR = 20% vs H_1 : ORR \neq 20%

The sample sizes will be further increased by 5% to account for patients who withdraw prematurely from the study. Hence, the total sample sizes will be 53 patients for Group 1, and 84 patients for Group 2, for a total of 137 patients. For each group, the actual minimum significant ORR at the end of study will be determined based on the final number of patients enrolled and treated.

2.4. Study Plan

After a screening period of up to 28 days, patients will receive up to 93 weeks of treatment. Each patient will receive a flat dose of 350 mg cemiplimab IV Q3W. Tumor assessments will be made at the end of each treatment cycle (5 treatment cycles of 9 weeks followed by 4 treatment cycles of 12 weeks). Extensive safety evaluations will occur on day 1 of each cycle, with routine safety evaluations to be conducted at each cemiplimab dosing visit.

A patient will receive treatment until the 93-week treatment period is complete, or until disease progression (PD), unacceptable toxicity, withdrawal of consent, or confirmed CR. Patients with confirmed CR after a minimum of 48 weeks of treatment may elect to discontinue treatment and continue with all relevant study assessments (eg, efficacy assessments). Patients who discontinue study treatment due to PD should return to the clinic 30 days (range: 21 days to 42 days) after the last study treatment to complete the end-of-study (EOS) assessments. After the EOS visit, patients should be followed for survival status until death, loss to follow up, or study termination by the sponsor.

3. ANALYSIS POPULATIONS

In accordance with guidance from the International Conference on Harmonization of Technical Requirements for Registration of Pharmaceuticals for Human Use (ICH) guideline ICH E9 Statistical Principles for Clinical Trials (ICH 1998), the following populations sets will be used for statistical analysis.

A patient is deemed eligible and enrolled after the patient completes the screening process and the first study drug dose is ordered in the interactive web response system (IWRS). At that point, the patient's status in IWRS changes from "in screening" to "enrolled." A patient is not deemed eligible until he/ she is enrolled in IWRS.

3.1. Full Analysis Set (FAS)

The full analysis set (FAS) includes all enrolled patients for each group who have passed screening and are deemed to be eligible for this study. All efficacy endpoints will be analyzed using the FAS by group.

Note: In the interim analysis of Group 1, only patients with sufficient follow up will be included in the FAS (refer to Section 8 for interim analysis of Group 1).

3.2. Safety Analysis Set (SAF)

The safety analysis set (SAF) includes all enrolled patients who have received any cemiplimab for each group. Treatment compliance/administration and all clinical safety variables will be analyzed or summarized using the SAF.

3.3. PK Analysis Set (PKA)

The PK analysis set (PKA) will include all patients who have received any cemiplimab and have at least one non-missing post-baseline measurement of cemiplimab concentration in serum.

3.4. Anti-Drug Antibody Set (ADA)

The anti-drug antibody set (ADA) includes all patients who have received any cemiplimab and who have at least one post-dose ADA result.

The NAb analysis set includes all patients who have received any cemiplimab and who have at least 1 non-missing result in the NAb assay.

3.5. Biomarker Analysis Set (BAS)

The biomarker analysis set (BAS) includes all patients who have received any cemiplimab and who have at least one sample assayed.

4. ANALYSIS VARIABLES

4.1. Demographic and Baseline Characteristics

The following demographic and baseline characteristics variables will be summarized:

- Age at screening in years (quantitative and qualitative variable: <65, ≥ 65 years)
- Sex (Male, Female)
- Race (American Indian/Alaskan Native, Asian, Black/African American, Native Hawaiian/Other Pacific Islander, White and Other)
- Ethnicity (Hispanic/Latino or not)
- Weight (kg)
- Height (cm)
- Body mass index (BMI) calculated from weight and height: $\text{weight (kg)} / [\text{height (m)}]^2$
- ECOG performance status (0, 1)

Baseline tumor characteristics variables include:

- Anatomic site at earliest known diagnosis
- Stage at initial diagnosis
- TNM stage at initial diagnosis and screening
- Metastatic status for Group 1 patients
- Time from initial diagnosis to first dose
- Time from most recent relapse/recurrence to first dose
- Time on prior HHI therapy

4.2. Medical History

Medical history will be coded to a Preferred Term (PT) and associated primary System Organ Class (SOC) according to the latest available version of MedDRA.

4.3. Pre-Treatment/Concomitant Medications and Procedures

Medications/Procedures will be recorded from the time of informed consent until 105 days after the last study treatment. This also includes medications and other therapies for which administration started before the study and will continue during the study, as well as any therapies started in the follow-up period to treat a study drug related AE. Medications will be coded to the anatomical therapeutic chemical (ATC) level 2 (therapeutic main group) and ATC level 4 (chemical/therapeutic subgroup), according to the latest available version of WHO Drug

Dictionary (WHODD). Patients will be counted once in all ATC categories linked to the medication.

Prior cancer related medications/procedures: medications taken or procedures performed prior to administration of the study drug, particularly, prior cancer related surgery, prior cancer related radiotherapy, and prior cancer related systemic therapy will be summarized.

Pretreatment medications/procedures: non-study medications for which administration started and discontinued before a patient received the first dose of study drug.

Concomitant medications/procedures: medications and other therapies that were ongoing at, or started between the first dose of study drug and 105 days after the last study drug, or started after 105 days after the last study drug to treat a study drug related AE.

Post treatment anti-cancer medications/procedures: anti-cancer medications and other anti-cancer therapies that started after initiation of the study drug.

4.4. Efficacy Variable

4.4.1. Primary Efficacy Variable

The primary objective of the study is to estimate the ORR for mBCC (Group 1) or laBCC (Group 2) according to central review. Objective response rate (ORR) by central review is determined by the proportion of patients with best overall response of CR or PR based on central-reviewed evaluation.

Overall response is determined by RECIST version 1.1 for visceral lesions (Appendix 1 of the protocol), or by modified WHO criteria for skin lesions (Appendix 2 of the protocol), or by the composite response criteria for patients with both visceral and skin lesions (Appendix 2 of the protocol) at each time point at which a response assessment occurs.

Best overall response (BOR) is determined once all the overall response data for the patient are known. The best overall response is the best response recorded during the study:

- Best overall response of CR or PR must be confirmed by consecutive evaluations of overall response of CR or PR at time points at least 4 weeks apart.
- Best overall response of SD must have met the response SD criteria at least once ≥ 39 days (6 weeks – 3 days) after start of study treatment. Best overall response of (early) PD does not require confirmation using the RECIST or the composite response criteria.
- The best overall response for patients who do not have any post-baseline tumor assessment will be not evaluable (NE). Patients with best overall response of NE will be considered as not reaching an objective response of CR or PR.

- Patients with inoperable BCC at baseline who are rendered operable with clear margins will be deemed to have experienced PR.

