7.7.1. Prohibited Medications and Procedures

While participating in this study, a patient may not receive any standard or investigational agent for treatment of a tumor other than cemiplimab as monotherapy. After communication with the sponsor, focal palliative treatment (eg, radiation) would be allowed for local control of a tumor once a patient has completed 24 weeks of study treatment. Patients must not receive live vaccines during the study and up to 5 half-lives after the last dose of study drug. Any other medication which is considered necessary for the patient's welfare, and which is not expected to interfere with the evaluation of the study drug, may be given at the discretion of the investigator.

Patients using immunosuppressive doses (>10 mg per day of prednisone or equivalent) of systemic corticosteroids other than for corticosteroid replacement will not be eligible for the study. It is recommended that patients do not receive systemic corticosteroids such as hydrocortisone, prednisone, prednisolone (Solu-Medrol[®]) or dexamethasone (Decadron[®]) at any time throughout the study except in the case of a life-threatening emergency and/or to treat an irAE. Physiologic replacement doses of systemic corticosteroids are permitted, even if >10 mg/day prednisone equivalents. A brief course of corticosteroids for prophylaxis (eg, contrast dye allergy) or for treatment of non-autoimmune conditions (eg, delayed-type hypersensitivity reaction caused by contact allergen) is permitted.

Note: Bisphosphonates and denosumab are not prohibited.

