8.1.4. Follow-up

Patients who discontinue study treatment due to PD should return to the clinic 30 days (range: 21 to 42 days) after the last study treatment to complete the EOS assessments indicated in [Table 4](#) (same as in [Table 5](#)), as appropriate. After the EOS visit, patients with PD should be followed for survival status until death, loss to follow-up, or study termination by the sponsor.

For all patients in Group 2, tumor biopsies ([Appendix 4](#)) should be obtained at time of progression, whether progression occurs in cycles 1 through 9 or during follow-up (after cycle 9).

Patients who discontinue study treatment due to reasons other than PD (eg, toxicity, confirmed CR after 45 weeks) should continue follow-up to complete all assessments in [Table 6](#) until PD or completion of follow-up visits 1 to 7 and extended follow-up ([Table 6](#)). After this time, patients will be followed quarterly for survival and tumor treatment status, if available, until death. Survival follow-up status may be determined at clinic visits or via telephone contact with the patient, a family member of the patient, or the physician.

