- **Group 2:** All externally visible BCC lesions should be photographed in a consistent manner at each response assessment as described in [Appendix 5](#). Radiologic imaging (MRI with gadolinium preferred) of anatomic area of externally visible target lesions should be performed at screening and at each response assessment. For each target lesion, the investigator will decide (based on screening imaging) if the radiology (CT or MR) or photo will be the most appropriate method to measure that target lesion, and should use the same modality to measure that target lesion at baseline and at each assessment. If photo is selected to measure a target lesion, imaging (CT or MR) should be obtained to provide supplemental information. In cases in which it is the opinion of the investigator that no significant added information was provided by baseline radiologic imaging of the lesion (beyond the information that was provided by baseline digital medical photography), it is allowed to use digital medical photography only (without radiologic imaging) at

subsequent response assessments of that lesion, at the discretion of the investigator (or vice-versa). If the investigator opts to discontinue cross-sectional radiologic imaging after the baseline assessments and follow the lesion only with digital medical photography (or vice-versa), the reason(s) should be captured in the CRF.

To account for the possibility of unconventional immune responses, immune-related response criteria (irRC) (Nishino 2013) can inform the decision regarding whether to continue treatment for an individual patient if the investigator believes it is in the best clinical interest of the patient, after discussion and approval from the medical monitor. Reasons for any such decision to treat beyond the protocol definitions of progression must be documented in the CRFs. When possible, progression should be confirmed. However, irRC are currently deemed a surrogate endpoint (Postow 2015), and irRC data are not included in the primary endpoint of this study. Any patient who experiences best response (PR or CR) after initial progression (per Appendix 1 or Appendix 2, as appropriate) in the context of continued treatment (according to principles of irRC in after sponsor approval) will not have that best response (partial or complete) counted towards the primary endpoint of this study.

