Although a clear progression of “non-target” lesions only is exceptional, the opinion of the treating physician should prevail in such circumstances, and the progression status should be confirmed at a later time by the review panel (or Principal Investigator).

Evaluation of Overall Response Criteria

The best overall response is the best response recorded from the start of the treatment until disease progression/recurrence (taking as reference for progressive disease the smallest measurements recorded since the treatment started). The patient’s best response assignment will depend on the achievement of both measurement and confirmation criteria. Revised Response Evaluation Criteria in Solid Tumors (RECIST) Version 1.1 ([Eisenhauer 2009](#)) are summarized in the table:

**Response According to Revised Response Evaluation Criteria in Solid Tumors
(Version 1.1)**

Target Lesions	Non-Target Lesions	New Lesions	Overall Response	Best Overall Response when Confirmation is Required^a
CR	CR	No	CR	≥4 weeks confirmation
CR	Non-CR/Non-PD	No	PR	≥4 weeks confirmation
CR	Not evaluated	No	PR	
PR	Non-CR/Non-PD/not evaluated	No	PR	
SD	Non-CR/Non-PD/not evaluated	No	SD	Documented at least once ≥4 weeks from baseline
PD	Any	Yes or No	PD	no prior SD, PR or CR
Any	PD*	Yes or No	PD	
Any	Any	Yes	PD	

CR=complete response; PD=progressive disease; PR=partial response; SD=stable disease.

^a In exceptional circumstances, unequivocal progression in non-target lesions may be accepted as PD.

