4.4.2. Secondary Efficacy Variables

ORR by investigator assessment is determined by the proportion of patients with best overall response of CR or PR based on investigator-assessed evaluation..

Duration of response (DOR) is determined for patients with BOR of CR or PR. DOR is measured from the time measurement criteria are first met for CR/PR (whichever is first recorded) until the first date of recurrent or progressive disease (photographic or radiographic), or death due to any cause.

- Patients who do not have a documented tumor progression or death will be censored at the last evaluable tumor assessment.
- Patients who do not have a documented tumor progression or death before initiation of new anti-cancer therapy will be censored at the last evaluable tumor assessment prior to or on the date of new anti-cancer therapy.
- Patients who do not have any evaluable post-baseline tumor assessment and do not die will be censored on the date of first study treatment.

Progression-free survival (PFS) is measured from the start of treatment until the first date of recurrent or progressive disease (photographic or radiographic), or death due to any cause.

- Patients who do not have a documented tumor progression or death will be censored at the last evaluable tumor assessment.
- Patients who do not have a documented tumor progression or death before initiation of new anti-cancer therapy will be censored at the last evaluable tumor assessment prior to or on the date of new anti-cancer therapy.
- Patients who do not have any evaluable post-baseline tumor assessment and do not die will be censored on the date of first study treatment.

Overall survival (OS) is measured from the start of treatment until death due to any cause. Patients who do not die will be censored at the last date that patient is documented to be alive. As many patients may receive new anti-cancer therapy after disease progression, a sensitivity analysis of OS will be conducted by censoring patients at the first date of a new anti-cancer therapy is taken.

Time to tumor response (TTR) is determined for patients with BOR of CR or PR. TTR is measured from the start of treatment until the time measurement criteria are first met for CR/PR (whichever is first recorded).

For all of the above time-to-event variables, the time to event (day) is the date of event/censor - the date of first study treatment + 1.

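### SAP 4.4.1 does not end best overall response at the start of new anti-cancer therapy, although the DOR and PFS rules in SAP 4.4.2 do

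*SAP*

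**What the plan says.** **Primary endpoint.** ORR by central review "is determined by the proportion of patients with best overall response of CR or PR based on central-reviewed evaluation" (SAP 4.4.1). The same section gives the window for best overall response (BOR): "The best overall response is the best response recorded during the study". Neither the primary analysis (SAP 5.8.1) nor the efficacy data conventions (SAP 6.2) add a cut-off.

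**Protocol limits on BOR.** Appendix 1 stops at progression: "The best overall response is the best response recorded from the start of the treatment until disease progression/recurrence". Section 8.2.2 adds that a patient treated beyond progression who responds later "will not have that best response (partial or complete) counted towards the primary endpoint of this study". Neither rule mentions new therapy. Appendix 2, which governs most Group 2 assessments, gives no BOR window.

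**DOR and PFS.** Under SAP 4.4.2, a patient without progression or death before new therapy is "censored at the last evaluable tumor assessment prior to or on the date of new anti-cancer therapy". The DOR start is also given there: "DOR is measured from the time measurement criteria are first met for CR/PR". The closing line of 4.4.2 then computes every time-to-event variable listed above it, DOR included, from the date of first study treatment.

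**Follow-up.** Protocol 8.1.4 keeps "Patients who discontinue study treatment due to reasons other than PD", for example because of toxicity, on the Table 6 assessments until progression or the end of follow-up. Under Table 6 footnote 10, follow-up scans depend only on progression not having been confirmed.

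**The concern.** The trial has one arm, and its efficacy claim is that cemiplimab monotherapy produced the responses. A response that starts after another anti-cancer therapy has begun cannot be attributed to cemiplimab in that way. The SAP recognises this for DOR, PFS, the OS sensitivity analysis and the on-treatment safety period (SAP 5.9.1), all of which use new therapy as a cut-off. The primary ORR does not.

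The documents also foresee the situation. SAP 4.3 defines a category for anti-cancer treatment begun after study drug. Protocol 8.1.5 makes retreatment conditional on no other systemic anti-cancer therapy having intervened, so it contemplates such therapy during progression-free follow-up.

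At stake are an ORR that can only be biased upward and responders whose DOR record contradicts itself.

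**Working it through.** **1. The plan's own figures reproduce.** The decision rule is a Clopper-Pearson 95% lower limit above 15% (Group 1) or 20% (Group 2). For x responders among n, the lower limit is the 2.5% quantile of Beta(x, n − x + 1). Power is P(X ≥ critical count) under the design ORR.
- Group 1, n = 50, design ORR 34%: critical count 14 (28%), power 85.2%.
- Group 2, n = 80, design ORR 35%: critical count 24 (30%), power 85.5%.

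Both match SAP 2.3. Sample size, alpha and power are not in question here.

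**2. One patient under the two rules.** Table 6 places imaging at follow-ups 2, 4 and 7, with visits 28 days apart. Suppose a patient stops cemiplimab for toxicity without progression and without an earlier response. New therapy starts just after follow-up 2, PR is first seen at follow-up 4, and it is confirmed at follow-up 7, which is 3 × 28 = 84 days later and so beyond the 4-week minimum.
- BOR under SAP 4.4.1: PR, so the patient is a responder in the primary ORR.
- DOR start: follow-up 4.
- DOR censoring date: follow-up 2.
- Censoring date minus onset: −(2 × 28) = −56 days.

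The closing formula in SAP 4.4.2 counts from first dose instead. If follow-up 2 falls on study day d, it returns d − 1 + 1 = d, a positive number. The formula hides the conflict, and it also disagrees with the DOR definition above it.

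**3. Effect at the decision boundary.**

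| Group | n | Responders | Lower limit | Benchmark | Result |
|---|---|---|---|---|---|
| 1 | 50 | 13 | 14.6% | 15% | fails |
| 1 | 50 | 14 | 16.2% | 15% | passes |
| 1 | 53 | 13 | 13.8% | 15% | fails |
| 1 | 53 | 14 | 15.3% | 15% | passes |
| 2 | 80 | 23 | 19.2% | 20% | fails |
| 2 | 80 | 24 | 20.3% | 20% | passes |
| 2 | 84 | 24 | 19.2% | 20% | fails |
| 2 | 84 | 25 | 20.3% | 20% | passes |

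**4. Illustration of the direction of bias, on assumptions.** Let f be the share of patients who do not respond to cemiplimab, start another therapy without progression and stay on study scans. Let r be the response rate to that therapy. If the true cemiplimab ORR equals the benchmark p0, the counted ORR is p0 + f × r. Neither f nor r is in the documents. For r I borrow the vismodegib rates in SAP 1.1.1 (30% metastatic, 43% locally advanced), which come from a different population and are probably too high here. The chance of a false success is then:

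| f | Group 1, ≥14/50 | Group 2, ≥24/80 |
|---|---|---|
| 0 | 0.013 | 0.022 |
| 2% | 0.018 | 0.034 |
| 5% | 0.028 | 0.063 |
| 10% | 0.054 | 0.145 |

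For example, Group 2 at f = 5% has a counted ORR of 0.20 + 0.05 × 0.43 = 0.2215. The one-sided nominal level is 0.025. These rows show direction and sensitivity; they do not estimate what will happen.

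**The case against.** **The route is narrow, and this stands.** Protocol 7.7.1 forbids other tumor agents while a patient is participating, so new systemic therapy followed by study scans would be a deviation if the patient still counts as participating. SAP 5.5 has deviations that affect efficacy identified before database lock. But 7.7.1 governs conduct and does not say how a response is counted, and SAP 5.5 only summarises deviations. Effective alternatives also look scarce: protocol 1.1 reports no approved agent after a hedgehog inhibitor and describes sonidegib after vismodegib as apparently inactive. An affected patient needs no progression, no earlier response, another effective therapy, continued scans and a confirmed response.

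**Central review may deal with it.** The protocol refers review processes to charter documents that are not available here. What can be said is that the SAP states no cut-off, not that the committee would ignore new therapy.

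**Stronger readings that the documents do not support.**
- A reader might infer that shrinkage of a locally treated target lesion counts as response, because "focal palliative treatment (eg, radiation) would be allowed for local control of a tumor once a patient has completed 24 weeks of study treatment". Protocol 7.7.3, however, deems radiation to be progression, surgery has its own PR rule (protocol 7.7.2, SAP 4.4.1), and 7.7.1 requires contact with the sponsor first. No text shows how any other focal treatment would be scored.
- A reader might infer that negative DOR values will appear in the output. They follow only from the prose definition; the closing formula gives positive values.
- A reader might take the boundary table as the likely size of the bias. It shows only what one responder does at the threshold, as would any misclassification there.

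**Conclusion.** The gap is real and narrow. By its literal wording, SAP 4.4.1 credits cemiplimab with a response that begins after another anti-cancer therapy in a patient without progression, while SAP 4.4.2 censors that patient's DOR before the response started. Ending BOR at progression, as Appendix 1 does, would not close it, because these patients have not progressed.

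The number affected is probably small and cannot be derived from the documents. The direction is certain: the omission can add responders but cannot remove any. One added responder matters only if a group lands at its threshold. The conclusion assumes that the SAP is applied as written and that no unseen charter rule overrides it. It should be fixed, but it does not invalidate the design or the sample size.

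**What to change.** In SAP 4.4.1:
- State that BOR uses assessments up to the earlier of first progression and the start of new anti-cancer therapy, matching DOR and PFS. Response onset must then precede that date.
- State in advance whether the confirming assessment may fall after the new therapy, and report the other choice as a sensitivity analysis. Either is defensible: excluding late confirmations discards responses that began on cemiplimab alone.
- Keep the clear-margin surgical PR as a separately stated exception, and say whether that surgery counts as new anti-cancer therapy for DOR.

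In SAP 4.4.2:
- Carry over the protocol 7.7.3 rule that radiation is deemed progression. The current DOR and PFS text recognises only photographic or radiographic progression.
- Reconcile the closing time formula with the DOR definition, so that DOR is counted from response onset.

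**Cost.** The changes are SAP wording and a date filter in the BOR derivation; sample size, alpha and power stay as they are. ORR may be slightly lower. Data collection also has to change: Table 6 footnote 11 requires cancer treatments to be recorded only until 105 days after the last dose, while Table 6 imaging continues through follow-up 7 (7 × 28 = 196 days on its schedule) and a further year of extended follow-up. Start dates of anti-cancer therapy must be captured for as long as tumor assessments continue.
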